#### • **Study Procedures**

All patients will be scanned by OCULUS Pentacam® HR, Germany and all of them will be subjected to topography-guided femto-Lasik using the FS200 (Alcon Wavelight, Erlangen, Germany) and EX500 devices (Alcon Wavelight, Erlangen, Germany). And all of them will be done by one surgeon.

#### • **Study Interventions**

All of them will undergo a complete ophthalmic examination to include or exclude cases, examinations including uncorrected distance visual acuity (UDVA) and corrected distance visual acuity (CDVA), IOP measurement, slit lamp examination, fundus examination, and Pentacam tomography.

At least 5 Pentacam scans will be taken for every patient each time. All Pentacam images will be collected and analyzed to measure the horizontal angle kappa, anterior astigmatism and its axis, back elevation data at the thinnest point, Anterior chamber depth and Axial length.

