## 1. INTRODUCTION/ REVIEW

Astigmatism has a corneal component and a lenticular component. Corneal astigmatism occurs when there are differences in the radius of curvature of the cornea in different meridians. ([Morlet et al, 2002](#)).

Astigmatism is classified as “with the rule” when the steep meridian on the corneal surface is between 60 and 120 degrees, and as “against the rule” when the steep meridian on the corneal surface is between 0 and 30 degrees or between 150 and 180 degrees. As the dioptric power of the posterior corneal surface is negative, posterior corneal astigmatism is classified as “with the rule” when the steep meridian on the corneal surface is between 0 and 30 degrees or between 150 and 180 degrees, and as “against the rule” when the steep meridian on the corneal surface is between 60 and 120 degrees. ([Koch et al, 2013](#)).

The magnitude of corneal astigmatism has been reported to vary with age. ([Attebo et al, 1999](#)). There is a shift of the steepest corneal meridian from the vertical (with-the-rule) to the horizontal meridian (against-the-rule). ([Mohammadi et al, 2016](#)).

The mean percentage and magnitude of astigmatism in the population aged 15

to 65 years are:  $\geq 0.5$  diopter (D) in 73.53%,  $\geq 1.0$  D in 32.78%,  $\geq 1.5$  D in 13.55%,  $\geq 2.0$  D in 6.86% and  $\geq 3.0$  D in 2.47%. (Gabor et al, 2013)

Angle kappa represents the angle between the visual and pupillary axes (Park et al, 2012). The visual axis connects the fovea with the fixation point and passes by the nodal point. The pupillary axis is the line passing through the center of the pupil perpendicular to the cornea. Angle kappa can be classified as positive (nasal) or negative (temporal). A positive angle kappa of  $5.0^\circ$  on average is generally found in the normal human eye. (Yeo et al, 2012).

Angle kappa decreases with age and tends to be larger in emmetropes and hypermetropes than in myopes). (Hashemi et al, 2010). But the relation of astigmatism to angle kappa still needs further studies. (Larysa et al, 2021).

Angle kappa is a crucial parameter in some surgical decisions. In keratorefractive surgery with a large angle kappa, there is a greater chance of decentration of ablation zones, and it may lead to negative visual effects such as high-order aberrations and under-correction. (Harrer et al, 2017 )

Angle kappa is a crucial parameter for proper centration of multifocal intraocular lens implantation. (Prakash et al, 2011)

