Higher angle kappa values have been recorded in exotropic patients when compared to esotropic patients. Ophthalmologists must take the kappa angle into account when performing a Hirschberg or Krimsky test in young and uncooperative patients in order to improve surgical results. (Niamh Stone et al, 2009)

The exact angle kappa is classically measured using a synoptophore. (Park, et al.2012). Newer instruments measuring angle kappa are applied in clinical practice such as Orbscan, OPD scan, and Pentacam. (Garzon et al, 2020)

The Pentacam system is a rotating Scheimpflug-based instrument that obtains a three-dimensional model of the anterior segment of the eye which indicates an

image from the anterior corneal surface to the posterior lens surface. The device captures up to 25 slit images of the anterior segment of the eye by a 360-degree rotating Scheimpflug camera, collecting 25, 000 true elevation data points (respecting 500 true elevation points per slit image) within 2 seconds. ([Chen and Lam, 2009](#)).

Elevation-based corneal imaging techniques provide valuable information about the posterior corneal surface elevation properties which important in the preoperative examination of refractive surgery, average elevation values For normal eyes, at the posterior apex and thinnest points were  $0.8 \pm 3.0 \mu\text{m}$  (SD) and  $3.6 \pm 4.7 \mu\text{m}$ , respectively. ([Koch et al, 2012](#)).

Pentacam measures angle kappa by measuring the distance between the pupil center and the first Purkinje image. ([Garzon et al, 2020](#))

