## 2. AIM/ OBJECTIVES :

The exact relation between anterior corneal astigmatism and angle kappa is still not scientifically understood.

The objectives of this study are to study:

The effect of treating astigmatism on angle kappa and corneal back elevation.

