### *- Inclusion Criteria:*

- Subjects aged 21 – 45 years from both sexes.

- myopia up to -8 D
- Corneal astigmatism up to -5 D.
- Stable refraction for 1 year before surgery.
- No ectasia.
- Corneal thickness of more than 500  $\mu\text{m}$ .
- Calculated residual stromal bed of more than 300  $\mu\text{m}$ .
- Axial length up to 30 mm.

- Exclusion Criteria:

None of the patients enrolled have:

- History of previous ocular surgery.
- History of previous ocular trauma.
- Corneal opacities within the central 7 mm.
- Moderate to severe dry eye diseases.
- Active or previous diseases linked to the anterior segment of the eye.
- Active or previous diseases linked to the posterior segment of the eye.
- Diabetic patients.
- Patients with collagen vascular diseases.
- Patients with glaucoma.
- Patients with post-operative complications

• **Sample Size** (100 eyes) will be divided equally into 2 groups:

- Group 1: subjects have anterior corneal astigmatism of -1.5 to -5 D.
- Group 2: subjects have anterior corneal astigmatism below -1.5 D.

• **Ethical Considerations**

The study will be conducted in accordance with the ethical standards stated by the ethical committee in the Faculty of Medicine- Ain Shams University,

with informed consent.

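### The objective concerns angle kappa as a whole, but only its horizontal component is extracted, so a vertical change would go undetected

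*Protocol*

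**What the plan says.** - **Objective.** Protocol section 2 (Aim/Objectives) gives the target as "The effect of treating astigmatism on angle kappa and corneal back elevation". The opening statement of what the study adds has the same scope. Neither limits angle kappa to one direction.
- **What the device measures.** Section 1 (Introduction/Review): "Pentacam measures angle kappa by measuring the distance between the pupil center and the first Purkinje image".
- **What will be extracted.** Section 3, Study Interventions: the images will be analysed to "measure the horizontal angle kappa, anterior astigmatism and its axis", followed by back elevation at the thinnest point, anterior chamber depth and axial length. No other angle kappa variable is named, and no reason is given for choosing the horizontal one.
- **Sign convention.** Section 1: "Angle kappa can be classified as positive (nasal) or negative (temporal"). This is a left–right convention.
- **Astigmatism axis.** Section 1 defines with-the-rule as a steep anterior meridian of 60–120 degrees, and against-the-rule as 0–30 or 150–180 degrees. The entry criterion "Corneal astigmatism up to -5 D" limits the magnitude but not the axis.

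**The concern.** The stated outcome and the recorded variable do not match. The position of one point relative to another in the frontal plane has a horizontal and a vertical part. If surgery moves the light reflex and the pupil centre relative to each other, the movement can lie in either direction or both. With only the horizontal part recorded, no change in that variable is compatible both with no effect on angle kappa and with a vertical effect.

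This matters more here than in a general survey of angle kappa, because astigmatism has a direction. In with-the-rule eyes the steep meridian is near vertical by the protocol's own definition, and nothing in the entry criteria excludes such eyes. A vertical change is therefore plausible enough to look for. The protocol also records the axis, but with one component the direction of a change cannot be related to it.

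This is not a detail that can be assumed to be left to an analysis plan. The protocol itself fixes which variables are taken from the scans.

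**Working it through.** The plan gives no effect size, standard deviation, alpha, power or expected shift for angle kappa, so it has no figure of its own to reproduce. Step 1 needs no assumption about the direction of a shift. Steps 2 to 5 are conditional.

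**1. What the recorded variable can show.** Let H and V be the horizontal and vertical parts of the offset between pupil centre and Purkinje image. The total distance is D = √(H² + V²). Surgery produces a change (ΔH, ΔV), and the plan records H only. When ΔH = 0, every value of ΔV gives the same recorded result, including ΔV = 0.

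**2. How much is lost if a shift follows the steep meridian (assumption, not in the protocol).** With the meridian at angle θ, the horizontal part of the shift's length is |cos θ| and the vertical part is |sin θ|. Means assume axes spread evenly within each band.

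| Band | Horizontal part, range | Horizontal part, mean | Vertical part, range |
|---|---|---|---|
| With-the-rule, 60–120° | 0 to 0.50 | 2(1 − sin 60°)/(π/3) = 0.256 | 0.87 to 1.00 |
| Oblique, 30–60° | 0.50 to 0.87 | (sin 60° − sin 30°)/(π/6) = 0.699 | 0.50 to 0.87 |
| Against-the-rule, within 30° of horizontal | 0.87 to 1.00 | sin 30°/(π/6) = 0.955 | 0 to 0.50 |

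**3. What this means for the whole sample.** Let p be the share of with-the-rule eyes.
- If the rest are against-the-rule, the mean horizontal part is 0.256p + 0.955(1 − p). It falls below one half when p exceeds (0.955 − 0.5)/(0.955 − 0.256) = 0.65.
- If the rest are split equally between against-the-rule and oblique, their mean is (0.955 + 0.699)/2 = 0.827. The threshold is then (0.827 − 0.5)/(0.827 − 0.256) = 0.57.

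The protocol does not give p.

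**4. Sign.** The means in step 2 ignore sign. If horizontal change is analysed with its sign, shifts on either side of 90 degrees cancel, and the mean of cos θ over 60–120 degrees is zero. The 26% figure therefore also depends on how change is defined.

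**5. Illustration of power.** The planned 100 eyes give 50 per group. Assume a two-sided 5% test, 80% power and the normal approximation. The detectable standardised difference is (1.960 + 0.842) × √(2/50) = 0.56. If only a fraction f of that difference appears in the horizontal component, with the same standard deviation, power is Φ(2.802f − 1.960):
- f = 0.87: about 68%
- f = 0.50: about 29%
- f = 0.26: about 11%

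The loss is small if the shift is mainly horizontal and large if it is mainly vertical. The protocol does not settle which applies.

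**The case against.** **The horizontal choice is a reasonable convention.** The introduction classifies angle kappa as nasal or temporal and cites a positive average of 5.0 degrees in normal eyes. This explains why the horizontal component was chosen. It does not justify dropping the other component when the question is whether surgery changes angle kappa.

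**The protocol says distance, not a two-dimensional displacement.** This is true, and the two components are an inference from its naming two points. It is a safe inference: the word horizontal in Study Interventions itself implies that the measure is resolved into directions.

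**The information is not destroyed.** The images are kept and the axis is recorded, so the vertical part could probably be extracted later, and axis could be brought in through an analysis plan that is not shown. This stands, and it limits the harm. A vertical outcome added after the horizontal result is known would, however, be post hoc.

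**A stronger reading is tempting.** A reader might infer that treatment in with-the-rule eyes acts on the vertical meridian, that a sample aged 21–45 years is mainly with-the-rule, and that the study will therefore miss most of the shift. The documents do not support this.
- No text says that a shift follows the treated meridian. Section 2 describes the relation between anterior astigmatism and angle kappa as not yet understood, and flattening symmetric about the centre need not move the reflex along that meridian.
- Myopia up to -8 D is admitted, so the surgery can include a spherical correction as well as the cylinder.
- On age, the introduction says only "There is a shift of the steepest corneal meridian from the vertical (with-the-rule) to the horizontal meridian (against-the-rule"). It gives no ages or proportions.
- The groups are formed by magnitude of astigmatism. The ratio 0.955/0.256 = 3.7 between against-the-rule and with-the-rule eyes therefore describes a comparison that the protocol does not set up.

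**Conclusion.** The point holds as a mismatch between objective and measurement. The objective covers angle kappa without restriction, and the only variable extracted is its horizontal component. If the plan is followed as written, a vertical change will not be detected, and a null horizontal result will not answer the question in section 2. That conclusion rests only on the protocol's text and on the fact that two points in the frontal plane can differ in two directions.

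The size of the loss is unknown. The figures of 0–50% retained in with-the-rule eyes and 87–100% in against-the-rule eyes rest on the added assumption that a shift lies along the steep meridian. The sample averages further require an axis distribution that the protocol does not give. They show that the loss could range from negligible to serious, and they do not estimate it. Since the direction of any effect is unknown, there is no stated basis for looking in one direction only.

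**What to change.** In Study Interventions, replace horizontal angle kappa with the horizontal component, the vertical component and the total distance between pupil centre and first Purkinje image, all taken from the same scans. Then:

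- Analyse the change in both components, preferably jointly, with total distance as a supplement. Distance alone would not show the direction of a change.
- Relate the change to the recorded astigmatism axis. State a sign convention for the vertical component beside the nasal/temporal one, and express the axis consistently across right and left eyes.

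If the vertical component is not wanted, restrict the objective and conclusions to horizontal angle kappa and give the reason.

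The first option should need no further scans or visits, assuming both coordinates can be read from the images already planned. Its cost is one more outcome to account for, which a joint two-component analysis handles. The second option costs only wording, but it narrows the question that the study can answer.

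### Does it matter that axial length is to be read from Pentacam images which, by the protocol's own account, stop at the back of the lens?

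*Protocol*

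**What the plan says.** Axial length appears twice in the protocol.

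- **Inclusion Criteria** (section 3): "Axial length up to 30 mm" is the last of eight criteria.
- **Study Interventions** (section 3): "All Pentacam images will be collected and analyzed to measure the horizontal angle kappa, anterior astigmatism and its axis", and the same sentence goes on to "back elevation data at the thinnest point, Anterior chamber depth and Axial length". Read grammatically, the Pentacam images are the source of every item in it.

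Two other places bear on whether this can be done.

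- **Study Procedures** (section 3) names the device: "All patients will be scanned by OCULUS Pentacam® HR, Germany".
- **Introduction** (section 1) says the device builds a "three-dimensional model of the anterior segment of the eye" and gives an "image from the anterior corneal surface to the posterior lens surface".

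The screening sentence in Study Interventions lists visual acuity with and without correction, then "IOP measurement, slit lamp examination, fundus examination, and Pentacam tomography". It names no biometer.

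**The concern.** Taken together, these statements assign a measurement to a device that, as the protocol describes it, does not see the far end of the distance. The protocol does not define axial length. In its ordinary meaning it ends at the retina, behind the posterior lens surface.

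If staff followed the sentence literally, one of the eight inclusion criteria could not be verified for any eye and a listed study variable would be empty for all 100 eyes. If they did not, the values would come from an instrument the protocol does not name, and two settings are listed.

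There is also an analytic worry. The Introduction reports that angle kappa tends to be smaller in myopes than in emmetropes and hypermetropes. A measure related to myopia could therefore help separate its influence from that of astigmatism, and it would be a pity to lose it.

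**Working it through.** The protocol gives no figure to reproduce and no arithmetic decides the point. The check is to compare the sections and then follow axial length to everything it could affect.

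**1. Is the inconsistency real?** Yes. The Introduction puts the end of the image at the posterior lens surface, while Study Interventions takes a cornea-to-retina distance from that image. No other source is given.

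**2. How many measurements are affected?** Counting the axis separately, the sentence lists six items: horizontal angle kappa, anterior astigmatism, its axis, back elevation at the thinnest point, anterior chamber depth and axial length. The first five lie between the front of the cornea and the lens, inside the stated range. The Introduction itself says the Pentacam obtains angle kappa from the pupil centre and the first Purkinje image. So 1 of 6 items is misattributed, and neither item named in the objectives is that one.

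**3. Does it follow that eligibility cannot be checked?** No. Eligibility rests on the screening sentence, which is separate from the sentence on image analysis and is worded as an open list. That list is visibly incomplete:

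| The criteria require | Named in the screening list? |
|---|---|
| Myopia limit and one year of stable refraction | No refraction named, though corrected acuity is |
| No moderate to severe dry eye | No dedicated test named |
| No diabetes or collagen vascular disease | No check named |
| Axial length limit | No biometer named |

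A list that omits several things the criteria plainly need cannot be taken as exhaustive. A criterion stated in millimetres implies that someone takes a reading.

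**4. What depends on axial length?**

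- Objectives (section 2 and the opening statement of purpose): angle kappa and corneal back elevation only.
- Grouping: 100 / 2 = 50 eyes per group, divided at an anterior corneal astigmatism of -1.5 D. Axial length plays no part.
- Statistical Analysis: names software only, with no adjustment for axial length.
- Who enters: myopia is already limited to -8 D, so the axial length limit probably excludes few additional eyes. The documents give no distribution of axial length, so this is a judgement and not a calculation.

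**The case for a change.** The strongest case for a change is that axial length is not simply left unassigned: the protocol assigns it to a source, and on its own description that source cannot supply it. An unlisted biometer would contradict that sentence, and a different Pentacam model would contradict the device description, so some wording is wrong either way. A statistical analysis plan would not normally settle which instrument decides eligibility.

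That much stands. The consequences drawn from it are weaker.

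- Complete loss of the variable requires staff to try to read axial length from images that do not contain it, and then to record nothing. The more likely course is that they use whatever biometry the clinic has.
- A difference in equipment between the two settings is conjecture. The document does not say where axial length is measured or that the instruments differ.
- The adjustment argument describes an analysis that one might like to see. This protocol does not plan it, so the slip does not damage it.
- Dropping the criterion and relying on refraction would alter an eligibility rule whose rationale the protocol does not give. It would also rest on a measurement that the screening list does not name either.

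**Conclusion.** The sections disagree, and the sentence in Study Interventions misstates where axial length comes from. This is a clerical slip affecting one of six listed measurements and the wording behind one of eight inclusion criteria. Naming the instrument would make the text consistent, but it would change no estimate of angle kappa or back elevation, no group assignment and no stated objective. No change to the plan follows, and the eligibility limit should be left as it stands.

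This rests on three assumptions:

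- axial length has its usual cornea-to-retina meaning;
- the screening list is illustrative, as its wording and omissions suggest;
- no analysis of the stated objectives depends on axial length. None appears in this document, and a statistical analysis plan is not at hand. If such an analysis were planned, the source of the readings would matter more than it does here.

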#### • **Statistical Analysis**

The results will be analyzed and discussed using Microsoft Excel and SPSS.

